Feasibility Testing (Aim 1): We will demonstrate feasibility, acceptability, and validity of the SPEEKO for Elderspeak feedback app use by staff in the NH and identify needed modifications prior to testing in Aim 2. The PI worked with the Speeko Company (see resources and letter) to develop the elderspeak feedback app. App proof of concept has been

demonstrated in the lab setting. With a preliminarily trained natural language processing detection model, diminutive accuracy testing resulted in a sensitivity (true positive rate) of 87.7% and a specificity (true negative rate) of 99.9%. The app provides immediate feedback with potential to increase CHATO effects. Recordings are analyzed by a natural language processing app that provides immediate and private feedback and encouragement to individual staff. The app detects common elderspeak terms of endearment (diminutives), identified through reanalysis of the PI's archived NH recordings.⁵⁶ Detection algorithms were also developed using the recordings to establish proof of concept. App modifications were completed to enhance recording quality and transcription accuracy and to filter noise.

Further feasibility and detection model algorithm optimization will be tested at Garden Terrace of Overland Park, a NH dedicated to dementia care. A detailed protocol and user manual will be developed, and pilot tested. Feasibility will be tested with five CNA volunteers (n=5) who will each record a 2-hour care session. These staff will record their speech during a 2-hour work session to demonstrate use of the feedback app and complete a 10-item usability scale. Potential issues (e.g., background noise, Internet and bandwidth adequacy, acceptability to residents) will be assessed. App outputs will be compared to data from transcription and psycholinguistic coding, using our established protocols, to validate app reliability for diminutive detection. The CNAs will be interviewed about use of the app, providing additional data to improve the system for Aim 2 testing. If validated, app functions may be expanded to monitor additional aspects of elderspeak (i.e., "we" pronoun substitutions).

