Data Archiving. After each recording session, the Project Director will screen and edit recordings to delete any resident or other staff communication or other identifiers (names) so that the archived recording contains only the desired CNA participant's voice. Recordings and data will be archived in a dedicated research computer labeled with unique identifier codes. To reduce the Hawthorne effect, the initial 15 minutes of each recording session will be discarded. An estimated hour of recorded speech will be collected four times for each of

60 CNAs, providing approximately 240 hours of recordings for transcription, coding, analysis, and additional app algorithm training.

Psycholinguistic Coding. RAs will transcribe all recordings (for both groups) and will use brackets to code diminutives using our established operational definitions and protocols.^{10,43,45,56,78} To assure reliability, as used in our past studies, RAs will be trained on a practice sample until achieving 90% agreement for utterance segmentation and coding. A second trained coder will independently code 10% of the actual study transcripts. Additional training will be provided if agreement falls below 85%. Systematic Analysis of Language Transcripts (SALT)⁷⁹ will be used to tabulate frequencies for each code. Data will be entered in an electronic spreadsheet using unique identifier codes and stored on a secure computer. RAs will not have access to the key connecting codes with identifying information and will be blind to group assignment and assessment time points.

Acceptability and Cost Testing (Aim 3): CNAs testing the app will complete the System Usability Scale (SUS), a validated 10-item industry standard survey to rate (1) use of the microphone, recorder, and app; (2) acceptability and work compatibility; (3) feedback infographic; and (4) interest in self-monitoring. We hypothesize that staff who use the app will find it acceptable and beneficial for their practice. As in our prior studies, we will use process-based costing to determine average costs for using the SPEEKO for Elderspeak feedback app, comparing costs relative to any difference determined for reductions in diminutive use in the immediate and delayed feedback groups.^{80,81} Evaluation of acceptability and costs are key factors in consideration of ongoing plans for app dissemination in NHs and across other long-term services and support settings.

C. Sample size, statistical methods, and power calculation

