Aim 1: We will demonstrate feasibility, acceptability, and validity of the SPEEKO for Elderspeak feedback app with detection model algorithm optimization with a diminutive accuracy testing benchmark of 80% or higher. App outputs will be compared to data from transcription and psycholinguistic coding, using our established protocols, to validate app reliability for diminutive detection. Also, an analysis of a CNA-completed, 10-item usability scale (The System Usability Scale) with an acceptability benchmark of 50% or higher.

Aim 2: Linear Mixed Models (LMMs) or Generalized LMMs, depending on the distribution of each outcome, will be developed to determine the impact of group assignment (feedback or no feedback) on use of elderspeak diminutives. Baseline diminutive use, group (feedback vs. no feedback), recording session (pre- and post CHAT sessions 1, 2, and 3), and interaction between intervention and session will be fitted as fixed effects. To account for clustering, each NH will be fitted as a random effect. To account for correlation due to repeated measurements, an appropriate covariance pattern will be determined from data. CNA and resident sex and CNA knowledge gain will be tested as covariates. Aim 2 will estimate variability, effect sizes, and intracluster correlation for a future larger-scale study. Sample sizes of as few as 30 in each group, or 10 CNAs on average in each NH, will achieve 80% power to detect a difference between the group means of 0.74 to 0.76 standard deviations, assuming the intracluster correlation coefficient ranging from 0.001 to 0.01 and coefficient of covariation among cluster sizes of 0.25. A two-tailed t-test was used with a significant level of 0.05 and the degrees of freedom based on the number of subjects.

Aim 3: We will use process-based costing to determine average costs for using the SPEEKO for Elderspeak feedback app, comparing costs relative to any difference determined for reductions in diminutive use in the immediate and delayed feedback groups.^{80,81}

D. Subject Criteria (See Vulnerable Populations appendix, if applicable):

1. Inclusion criteria: We will recruit CNAs who are age 18 or older, permanent employees, and fluent in English to participate. Descriptive information (age, sex, race, ethnicity, role, experience) will be used to identify CNA covariate factors predicting communication

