1. The PI and other research team members as delegated will conduct an audit at least annually including review of a random sample of at least 3 CNAs who participate in CHATO training and participate in audio recording for compliance with study protocols including informed consent documents, data storage documentation and deidentification of data. The PI will conduct an annual review of research team member compliance with IRB required training and certification. The PI or delegate will train and supervise research team members in recruitment and consenting procedures, data collection, provision of intervention, and data analysis and coding on a quarterly basis. Specific procedures to assure fidelity and compliance with the protocol are included in the research plan.
2. The **SMC** will initially review and approve the written study protocol, data collection and storage protocols, intervention materials, informed consent procedures, and this plan for data and safety monitoring. Any outside agreements with vendors and subcontractors will be reviewed. The SMC will also review the general reporting guidelines based on the study procedures approved by IRB. Reporting rules will be established taking into consideration the population under study and anticipated

adverse outcomes (reflected in the human subjects consent documents). Prior to study implementation, the SMC will identify pre-specified stopping rules that will be employed if significant benefits or risks have developed, if trial management issues prevent successful completion, or if compelling ethical concerns arise.

V. Data Analysis and Reporting

A. Statistical and Data Analysis:

1. **AIM 1.** Demonstrate feasibility, acceptability, and validity of the SPEEKO for Elderspeak feedback app use by staff in the NH. Five certified nursing assistants (CNAs) will use the app during NH care and provide feedback about any needed modifications. **Analysis:** A 10-item usability scale. Success will be determined by a cumulative score of 80% or more.
2. **AIM 2.** Test preliminary effects of an innovative self-monitoring feedback app on staff elderspeak use and compare accuracy to psycholinguistic analyses of audio-recorded staff communication. **Statistical Analysis:** Linear Mixed Models (LMMs) or Generalized LMMs, depending on the distribution of each outcome, will be developed to determine the impact of group assignment (feedback or no feedback) on use of elderspeak diminutives.

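### Aim 1 gives two unreconciled criteria for the same 10-item usability scale: 50% or higher in II.C, and a score of 80% or more in V.A.1

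*Combined protocol and SAP*

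**What the plan says.** Section II.B (Feasibility Testing, Aim 1) sets out the step: "Feasibility will be tested with five CNA volunteers (n=5) who will each record a 2-hour care session". These CNAs "demonstrate use of the feedback app and complete a 10-item usability scale". No second usability scale is described for them. The CNAs are also interviewed about using the app, and practical issues are assessed. The purpose given is to "identify needed modifications prior to testing in Aim 2".

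Section II.C (Sample size, statistical methods, and power calculation), under Aim 1, names two benchmarks. One concerns the app's accuracy: "detection model algorithm optimization with a diminutive accuracy testing benchmark of 80% or higher". The other concerns the CNAs' ratings: a "10-item usability scale (The System Usability Scale) with an acceptability benchmark of 50% or higher".

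Section V.A (Statistical and Data Analysis), item 1, states the Aim 1 analysis in two sentences: "A 10-item usability scale. Success will be determined by a cumulative score of 80% or more". It does not mention the accuracy benchmark or the 50% figure.

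Under Aim 3, section II.B describes the instrument as the "System Usability Scale (SUS), a validated 10-item industry standard survey" and gives no threshold there.

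**The concern.** Two sections set a numeric criterion for the same aim, participants and questionnaire, and the numbers differ. Neither is presented as an amendment of the other, and no section describes a minimum and a target. V.A calls its figure a score. II.C does not say what its 50% is a percentage of.

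Acceptability is a named part of Aim 1, and these two sentences hold its only numeric criteria. For a middling result, the reported verdict would depend on which section is cited. While the text stands, that choice could be made after the five ratings are known. This is a possibility the wording leaves open; nothing in the documents suggests it is intended.

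**Working it through.** Neither threshold is derived from a formula or stated inputs, so there is no plan figure to reproduce. The check compares the two texts and then works out the consequence under each reading.

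**Same object?**

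| | II.C, Aim 1 | V.A, item 1 |
|---|---|---|
| Instrument | 10-item System Usability Scale | a 10-item usability scale |
| Respondents | CNAs (five, from II.B) | five CNAs |
| Threshold | 50% or higher | 80% or more |
| Label | acceptability benchmark | success, by cumulative score |
| Metric | not stated | a score |

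II.B gives the Aim 1 CNAs one 10-item scale, so both rows of thresholds apply to the same five questionnaires.

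**Reading 1: both figures are scores, as a percentage of the maximum.**
- Gap: 80 − 50 = 30 percentage points.
- The sections disagree when 50 ≤ result < 80.
- As a total over five CNAs, the maximum is 5 × 100 = 500. The thresholds are 0.50 × 500 = 250 and 0.80 × 500 = 400, so the sections disagree for totals from 250 to just under 400.

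To see how often that could happen, assume a true mean μ and between-CNA standard deviation σ on the percentage scale. These are assumptions; the documents give neither. With a normal approximation (rough for five bounded scores), P(mean of five ≥ t) = 1 − Φ((t − μ)/(σ/√5)). For μ = 70 and σ = 20, the standard error is 20/√5 = 8.94. P(≥ 50) = 1 − Φ(−2.24) = 0.987 and P(≥ 80) = 1 − Φ(1.12) = 0.132. Any result that meets 80% also meets 50%, so the chance of conflicting verdicts is the difference, 0.855.

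| Assumed true mean | P(meets 50%), SD 10 / 20 | P(meets 80%), SD 10 / 20 | P(sections disagree), SD 10 / 20 |
|---|---|---|---|
| 60 | 0.987 / 0.868 | 0.000 / 0.013 | 0.987 / 0.855 |
| 70 | 1.000 / 0.987 | 0.013 / 0.132 | 0.987 / 0.855 |
| 80 | 1.000 / 1.000 | 0.500 / 0.500 | 0.500 / 0.500 |

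**Reading 2: II.C's 50% is a share of CNAs and V.A's 80% is a score.** The 50-to-80 band does not apply. II.C would need at least 0.5 × 5 = 2.5, that is 3 of 5 CNAs, but it does not say what a CNA's rating must reach to count, so its verdict cannot be computed. V.A would still tie success to a different quantity from the one benchmarked in II.C.

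**Reading 3: both are shares of CNAs.** This sits badly with V.A's reference to a score. If taken, 50% needs 3 of 5 and 80% needs 0.8 × 5 = 4 of 5, so exactly 3 of 5 would give opposite verdicts.

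No reading makes the two sections agree for every possible result.

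**The case against.** The best defence is that the labels differ. An acceptability benchmark of 50% could be a floor and success at 80% a target, or the 50% could be a share of CNAs. Either could be what was meant, but neither is written anywhere. V.A's Aim 1 objective itself includes acceptability and names the usability scale as its only analysis, so its 80% is applied to the property that II.C benchmarks at 50%. What stands is that a remedy should not rule these readings out.

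A second defence is that little depends on the number. Five people are involved, the step exists to find modifications, and the CNA interviews also bear on acceptability. That is correct and limits the weight of the point. It does not remove the conflict, because V.A says success is determined by the score.

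Three stronger readings are tempting, and the documents do not support them.
- A reader might infer that the conflict threatens the cluster randomised comparison. No section makes Aim 2 conditional on the usability score, and the Aim 2 power statement and model do not use it.
- A reader might infer a second error, that the rule for combining five scores is absent. V.A's reference to a cumulative score already points to a pooled total. For five complete scores, total/500 as a percentage equals the mean percentage. This is at most missing detail.
- A reader might infer that Aim 1 has no validity criterion because V.A omits one. II.C supplies it: "a diminutive accuracy testing benchmark of 80% or higher".

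That same 80% suggests that V.A's figure may have been carried over from the accuracy benchmark. This is plausible but unconfirmed. If true, V.A attaches the wrong criterion to the usability scale and still needs correcting.

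**Conclusion.** The contradiction is real and is in the current text. If both figures are percentage scores, the thresholds differ by 30 points and every result from 50% to just under 80% passes one section and fails the other. Under the assumed true means of 60 to 80 and standard deviations of 10 to 20, the sections would disagree with probability of about 0.50 to 0.99. These probabilities are only illustrations. If II.C's 50% is on another metric, the band falls away and what remains is an undefined benchmark beside a different statement of what determines success.

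The consequence is confined to the usability-score part of the Aim 1 conclusion, in a five-person feasibility step. The documents do not show which figure was intended. The correction is worth making because it is cheap and should precede the data.

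**What to change.** Before Aim 1 data are seen, reconcile II.C and V.A, item 1:

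1. State the one usability criterion that determines Aim 1 success, with its metric, in identical words in both sections. The investigators choose the value. Possible wording, if the metric is the score: *Aim 1 usability success: the five CNAs' combined System Usability Scale score, as a percentage of the maximum possible, is at least [single value].*
2. If both figures are meant to stand, say what each measures and which one determines success.
3. Check whether the 80% in V.A was meant for the detection-accuracy benchmark. In either case, V.A can cross-refer to that benchmark in II.C.

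Cost: protocol wording only, with no added participants, data or procedures. If both figures are scores, one stated criterion moves by 30 points: keeping 80% is stricter than II.C now says, and keeping 50% is easier than V.A now says. If they are on different metrics, the cost is only the added definitions.

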3. **AIM 3.** Evaluate app acceptability and costs. **Analysis:** Process-based costing to determine average costs for using the SPEEKO for Elderspeak feedback app, comparing costs relative to any difference determined for reductions in diminutive use in the immediate and delayed feedback groups.

B. Outcome:

1. **AIM 1 Expected Outcome:** The app will be readily used and acceptable to CNAs. Diminutive counts determined by the app will be correlated with psycholinguistic analysis, validating accuracy.
2. **AIM 2 Expected Outcome:** Staff who receive immediate app feedback (N= 30 in three NHs) will have greater elderspeak reduction after completing CHATO training compared to delayed feedback controls (N= 30 in three NHs).
3. **AIM 3 Expected Outcome:** Staff who use the app will find it acceptable and beneficial for their practice. Process-based costing will be used to determine costs for app use in NHs and other long-term service and support settings. Costs will be compared in relation to each group's outcomes.

C. Study results to participants: Audio recording feedback via the app will be provided either immediately after recording (treatment group) or at the end of the study (control group). Nursing homes will receive CHATO participation rate feedback.

D. Publication Plan: The PI will develop an appropriate plan for publication of research results based on the study aims and results.

VI. Bibliography / References / Literature Cited

1. Department of Health and Human Services. *National plan to address Alzheimer's disease: 2015 Update*. 2015.
2. Alzheimer's Association (2017). Alzheimer's Disease Facts and Figures.

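### Sections II.C and V.A.1 give different rules for Aim 1 success, and the V.A.1 rule omits the plan's own diminutive accuracy benchmark

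*Combined protocol and SAP*

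**What the plan says.** Three sections bear on Aim 1 success, and a fourth on what follows from it.

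- **V.A Statistical and Data Analysis, item 1** restates the aim as "Demonstrate feasibility, acceptability, and validity of the SPEEKO for Elderspeak feedback app use by staff in the NH". It then gives a single analysis and a single rule: "A 10-item usability scale. Success will be determined by a cumulative score of 80% or more". It has no criterion for detection.
- **II.C Sample size, statistical methods, and power calculation, Aim 1** optimises the detection model "with a diminutive accuracy testing benchmark of 80% or higher" and plans that "App outputs will be compared to data from transcription and psycholinguistic coding, using our established protocols, to validate app reliability for diminutive detection". It also analyses the System Usability Scale "with an acceptability benchmark of 50% or higher".
- **V.B Outcome, item 1** expects that "Diminutive counts determined by the app will be correlated with psycholinguistic analysis, validating accuracy". It gives no threshold.
- **II.B, Feasibility Testing (Aim 1)** says the team will "identify needed modifications prior to testing in Aim 2". The only consequence it ties to validation is that "If validated, app functions may be expanded to monitor additional aspects of elderspeak".

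**The concern.** V.A.1 is the only place that says how Aim 1 success is determined. It disagrees with II.C in two ways: the usability cut-off is 80% rather than 50%, and the accuracy benchmark is absent. An analyst following V.A.1 as written could report that Aim 1 succeeded, an aim that includes validity, for an app that had missed the plan's accuracy benchmark.

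Usability cannot stand in for accuracy. As II.B describes it under Acceptability and Cost Testing, the scale covers the equipment and app, fit with work, the infographic and interest in self-monitoring. It does not cover whether the displayed counts are right, and nothing says the five CNAs will see the coded transcripts.

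This matters because the app's diminutive count is the feedback given to the immediate-feedback group in Aim 2. The laboratory sensitivity of 87.7% came from a preliminary model, and II.B lists background noise and Internet adequacy among the issues still to be assessed in the nursing home. Aim 1 is the only planned check at the point of care before Aim 2.

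**Working it through.** The thresholds are set benchmarks, not the output of a power or error-rate calculation, so there is no figure to reproduce. The check applies each section's criteria to the same hypothetical results.

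**Criteria**

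- V.A.1: success if usability ≥ 80%.
- II.C: met if accuracy ≥ 80% and usability ≥ 50%. Reading the two jointly is an assumption; II.C lists both without saying how they combine.

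**Results**

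| Usability | Accuracy | V.A.1 | II.C | Agree? |
|---|---|---|---|---|
| 45% | 60%, 79%, 80% or 87.7% | fail | not met | yes |
| 65% | 60% or 79% | fail | not met | yes |
| 65% | 80% or 87.7% | fail | met | **no** |
| 85% | 60% or 79% | success | not met | **no** |
| 85% | 80% or 87.7% | success | met | yes |

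The sections conflict in two regions:

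1. Usability ≥ 80% with accuracy < 80%: V.A.1 passes, II.C does not.
2. Usability from 50% to below 80% with accuracy ≥ 80%: II.C is met, V.A.1 fails.

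**Would settling the usability cut-off be enough?** At a common 80%, usability 85% with accuracy 60% still passes V.A.1 and misses II.C. At a common 50%, usability 65% with accuracy 60% does the same. Region 2 disappears; region 1 remains, because V.A.1 has no accuracy term. The exception is if the 80% in V.A.1 was meant as the accuracy benchmark. Correcting that would restore the accuracy term, and the usability criterion would then have to be added back.

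**Would the accuracy benchmark make a difference?** For illustration, take accuracy to mean sensitivity and let K be the total number of true diminutives in the five sessions, treated as independent. The documents give no K, so 20 to 200 is an assumed range. The chance of observing at least 80% is P(X ≥ 0.8K) with X ~ Binomial(K, true sensitivity):

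| K | True sensitivity 70% | True sensitivity 87.7% |
|---|---|---|
| 20 | 0.2375 | 0.91 |
| 50 | 0.0789 | 0.962 |
| 100 | 0.0165 | 0.9905 |
| 200 | 0.0009 | 0.9993 |

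Under these assumptions the II.C benchmark would usually separate a poor detector from one performing as in the laboratory. Diminutives clustered within five speakers would make the separation less sharp. The V.A.1 result is the same at every accuracy.

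**The case against.** The strongest reply is that the validity criterion is already in the plan. II.C is itself a statistical methods section and sets the 80% accuracy benchmark; II.B plans the comparison with coding; V.B.1 lists agreement with coding as an expected outcome. An app below 80% misses a stated Aim 1 benchmark and counts as a success only if V.A.1 is read alone. V.A also looks like a shortened restatement: item 2 drops the model terms given in II.C, and item 3 names acceptability but lists only costing. Silence there is weak evidence that something was excluded.

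Much of this stands, and it limits the finding. It does not remove it. V.A.1 is more than silent: it states a decision rule, with a usability cut-off that differs from II.C, so it cannot be a mere abbreviation of II.C.

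Three stronger readings are tempting, and the documents do not support them.

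- A reader might infer that V.A.1 sends a failing app into Aim 2. No section makes Aim 2 depend on the V.A.1 score, on the II.C benchmarks or on both. An inaccurate app could go forward because no consequence is stated, not because V.A.1 directs it.
- A reader might infer that an app missing half the diminutives would show a CNA an apparent halving. The immediate-feedback group is shown counts only after post-CHATO sessions, so there is no displayed baseline to fall from. Constant under-detection would understate each count alike.
- A reader might infer that a null Aim 2 result could not be interpreted. Aim 2 compares app results with psycholinguistic coding again, and research assistants code all recordings in both groups, blind to group and time point. A null result can be read beside that measured accuracy, though only after any faulty feedback has been given.

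**Conclusion.** The concern holds as a contradiction between II.C and V.A.1, together with an unstated consequence for Aim 2. In one region (usability ≥ 80%, accuracy < 80%) V.A.1 would report success where the plan's own validity benchmark is missed. In the other (usability from 50% to below 80%, accuracy ≥ 80%) it would report failure where both II.C benchmarks are met. This rests on reading the two II.C benchmarks jointly and V.A.1 as written. How likely either result is cannot be judged from the documents.

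The exposure is to the Aim 1 conclusion and to the quality of the feedback delivered in Aim 2. It is not mainly to outcome measurement, since diminutives are hand-coded in both groups. Whether the 80% in V.A.1 is a deliberate usability cut-off or a misplaced accuracy benchmark remains open; V.A.1 needs rewriting in either case.

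**What to change.** Reconcile II.C and V.A.1 into one rule and state it identically in both, for example:

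> Aim 1 is successful only if (a) diminutive detection meets the II.C accuracy benchmark against psycholinguistic coding of the five sessions and (b) the System Usability Scale score meets the single agreed cut-off. The two components are reported separately.

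The sponsor should state which usability cut-off is intended and whether the 80% in V.A.1 referred to usability or accuracy.

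Add that the coding of the five sessions will be finished and reviewed against the benchmark before Aim 2 recording starts, and say what follows if it is missed. The modifications that II.B promises before Aim 2 would then rest on accuracy as well as usability. Making Aim 2 wait until the exact app version to be used has met the benchmark is a further option, but a design choice that the documents do not require.

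The cost is protocol wording and the timing of coding already planned; no extra data are needed. The downside is that Aim 1 can now fail on accuracy, and Aim 2 may be delayed while the app is corrected.
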